**D. STATISTICS ANALYSIS**

Data was analyzed using SPSS Version 25. All quantitative information are expressed as mean values  $\pm$  standard deviation (SD). Statistical significance was assessed using unpaired Student's t-test or chi-square test. Probability values of less than 0.05 were considered significant and an asterisk identifies such significance in the figures. We will also compare the adverse effect of each group using descriptive statistics.

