## B. STUDY METHOD AND DESIGN

- 330 women with menstrual disorders were observed in a prospective multi-center randomized controlled clinical trial.
- Inclusion Criteria:
  - 1) Aged between 25 and 40 years old;
  - 2) Patients with oligomenorrhea or oligomenorrhea or menopause within three months (see Appendix 1: Diagnostic Criteria of Traditional Chinese and Western Medicine)
  - 3) Meet the clinical medication conditions for progesterone to regulate menstruation
  - 4) The research subjects were informed and voluntarily participated in this study, and signed the informed consent at the same time.
- Exclusion Criteria:
  - 1) Age <25 years or >40 years old, pregnant or breastfeeding women
  - 2) Ovarian dysfunction caused by local ovarian surgery, radiotherapy and

chemotherapy for previous malignant tumors, taking hormones or immunosuppressive drugs;

- 3) Combined with serious or unstable physical diseases that may affect the efficacy of drugs and the conduct of trials, including liver, kidney, gastrointestinal, cardiovascular, respiratory, endocrine, neurological, immune or blood system diseases, etc., mental patients .
- 4) Those who were allergic to the drugs used in the trial or had serious adverse reactions in the past;
- 5) Breast cancer or family history of breast cancer in first-degree relatives, irregular vaginal bleeding, uterine fibroids ( $\geq 3$ cm), endometriosis, atypical endometrial hyperplasia, endometrial cancer and other hormone-dependent reproduction Systemic diseases and other malignant tumors;
- 6) Those with a history of thromboembolic disease or thrombosis;
- 7) Participated in a clinical trial of another research drug within 3 months prior to inclusion in this study (the first interview);
- 8) Those who have used related drugs in the past 3 months or have abused or depended on substances (alcohol or drugs) in the past 3 months; heavy smokers (smokers who smoke 20 or more cigarettes per day);
- 9) Those who met the inclusion criteria, did not follow the doctor's advice, were unable to judge the curative effect or were unable to evaluate the curative effect due to incomplete data.

➤ Methods: The participants were divided randomly into 3 groups:

- 1) Experimental group1(Zhenqi Buxue Oral Liquid): Zhenqi Buxue Oral Liquid, 10 ml each time, 2 times a day for 3 menstrual cycles, orally

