- 2) Experimental group2(Zhenqi Buxue Oral Liquid and Progesterone Capsules): Zhenqi Buxue Oral Liquid was taken orally, 10 ml at a time, twice a day for 3 menstrual cycles + orally from the second half of menstrual cycle, Progesterone Capsules 200mg, once a day for 10 days for 3 menstrual cycles
- 3) Active Comparator group (Progesterone Capsules): Progesterone Capsules 200mg, qd\*10 days\*3 menstrual cycles, orally

- Treatment Period: 3 month.
- Outcomes Measurement:
  - 1) Primary Outcome: Menstrual improvement in women including cycle period, menstrual volume, number of days with bleeding or spotting, monthly rates of amenorrhea
  - 2) Secondary Outcome:
    - a) Sex hormone levels: mainly FSH, LH, E2 and AMH
    - b) AFC: Changes in AFC in pelvic ultrasonography
    - c) SF-36: The change of the MOS item short from health survey
  - 3) Safety Assessment: Adverse reactions, Hepatic Function, Renal Function, Blood Glucose, Breast Ultrasound

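### Student's t-test on raw means is the only test named for quantitative outcomes: it probably costs power on the hormones, and it can exceed 5% error on cycle period if the more variable group is the smaller one

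*Combined protocol and SAP*

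**What the plan says.** Section D (Statistics Analysis) is the whole analysis plan. On summaries it says "All quantitative information are expressed as mean values" with the standard deviation. On testing it says "Statistical significance was assessed using unpaired Student's t-test or chi-square test", and on the threshold "Probability values of less than 0.05 were considered significant". It mentions no check of distribution or variance, no transformation, no rank test and no unequal-variance form of the t-test.

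The rule therefore covers two kinds of outcome listed in Section B:
- The first secondary outcome, "Sex hormone levels: mainly FSH, LH, E2 and AMH".
- Cycle period, which is one component of the primary outcome.

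Section B also says "The participants were divided randomly into 3 groups". Group 1 takes the oral liquid alone, group 2 takes it with a 10-day progesterone course each cycle, and group 3 takes the progesterone course alone ("Progesterone Capsules 200mg, qd"). The total is 330 women. No allocation ratio, dropout rate, SD or outcome distribution is given.

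**The concern.** Two features of these outcomes fit poorly with an equal-variance t-test on raw values.

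**Hormones.** Concentrations cannot be negative and often have a long upper tail. A few high values then inflate the SD, and a real shift between groups is harder to detect than on the log scale. What is at stake is power on four secondary outcomes.

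**Cycle period.** Groups 2 and 3 receive a progesterone course each cycle and group 1 does not, so the spread of cycle length in group 1 may differ from the other two. Student's t pools the variances. If the more variable group has fewer analysed women, the pooled standard error is too small and the test rejects too often. What is at stake is the error rate on a component of the primary outcome, in 1 v 2 and 1 v 3. Both groups in 2 v 3 receive progesterone, so this reasoning does not reach that comparison.

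**Working it through.** The plan has no figure of its own to reproduce, because the sample of 330 comes without a power calculation.

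**Inputs from the documents:** 330 women, 3 groups, 0.05 threshold.

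**Assumed:** equal allocation (330/3 = 110 per group), two-sided tests, log-normal hormones with log-SD σ from 0.4 to 1.0, and cycle SD of 15 days in group 1 v 5 days in a progesterone group (10 v 5 as a milder case).

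**1. Hormones: power on the raw and log scales**

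Reference effect: a shift of δ = 0.378σ on the log scale. Log-scale power = Φ(0.378 × √(110/2) − 1.96) = Φ(2.803 − 1.96) = Φ(0.843) = 80%.

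The coefficient of variation of a log-normal variable is CV = √(exp(σ²) − 1). The same shift, as a standardised raw difference, is

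d_raw = (exp(δ) − 1) / (CV × √((1 + exp(2δ))/2)), with approximate power Φ(d_raw × √55 − 1.96).

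For σ = 0.8: δ = 0.302, exp(δ) = 1.353, CV = 0.947, so d_raw = 0.353/(0.947 × 1.190) = 0.313 and power ≈ Φ(2.32 − 1.96) ≈ 64%.

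| log-SD | ratio of geometric means | d_raw | power, formula | power, simulated |
|---|---|---|---|---|
| 0.4 | 1.163 | 0.361 | 76.4% | about 77% |
| 0.6 | 1.255 | 0.341 | 71.5% | about 73% |
| 0.8 | 1.353 | 0.313 | 64.2% | about 67% |
| 1.0 | 1.459 | 0.280 | 54.7% | about 60% |

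The normal approximation is too pessimistic at strong skew, so the simulated column is the one to use. In the same simulations the log-scale t-test has 79% to 80% power. A Mann-Whitney test has 77% to 79% (log-SD 0.4 to 1.2). The relative efficiency of the raw test is 0.925 at log-SD 0.4 and 0.632 at 1.0. So 110 women per group analysed raw are worth about 110 × 0.925 = 102, or 110 × 0.632 = 70, analysed on the log scale. Type I error of the raw test is 4.3% to 5.0% (log-SD 0.4 to 1.2).

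**2. Cycle period: type I error of Student's t**

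The true variance of the difference is s1²/n1 + s2²/n2. In large samples the pooled estimate tends to s1²/n2 + s2²/n1. With R the ratio of the first to the second, the actual two-sided error is 2 × (1 − Φ(1.96/√R)).

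- 110 v 110: R = 1, error 5.0%.
- 99 v 110, SD 15 v 5: R = (225/99 + 25/110)/(225/110 + 25/99) = 2.500/2.298 = 1.088; 1.96/1.043 = 1.879; error 6.0%.
- 77 v 110, SD 15 v 5: R = (225/77 + 25/110)/(225/110 + 25/77) = 3.149/2.370 = 1.329; 1.96/1.153 = 1.700; error 8.9%.

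Simulation gives 5.1%, 6.1% and 9.0%, with Welch's test at about 5% each time. With SD 10 v 5, the error is 5.8% at 99 v 110 and about 7.8% at 77 v 110. If the more variable group is the larger (110 v 77, SD 15 v 5), Student's t is conservative at about 2.4%.

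**3. If the missing cycles are the long ones**

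With equal true means, SD 15 v 5, and the longest 10% of group 1 unobserved, Student's and Welch's tests both reject in just over half of trials. With the longest 30% unobserved, the group 1 mean shifts by about −7.4 days and both reject nearly always.

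**The case against.** The strongest reply is that the documents give no distribution or variance for any outcome, so skew and unequal spread are both assumptions. That is correct, and some features may limit them. Section B excludes endocrine disease and ovarian dysfunction after surgery, radiotherapy or chemotherapy, and Section C fixes the hormone sample on cycle day 2 or 3. At log-SD 0.4 the loss is only about 3 points. The comparison also assumes that treatment acts by a ratio. The size of the loss is therefore conditional, but the direction is secure for any clearly right-skewed hormone with a proportional effect.

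The timing argument for cycle period is also thin. Group 2's course is placed relative to the woman's own cycle, and no start is given for group 3. This too stands, so a different spread is possible and not established.

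A reader might infer more than the documents support in four ways:
- **That the raw hormone tests are invalid.** They are not; only power is lost.
- **That mean ± SD implies impossible negative hormone values.** For log-normal data, mean minus SD is negative only when CV exceeds 1, that is σ > √(ln 2) = 0.83. At log-SD 0.4, 0.6 and 0.8 it is positive.
- **That the cycle-period test is wrong as planned.** With equal groups it holds about 5%. Unequal analysed numbers are possible, because the allocation ratio is unstated, women without a period have no completed cycle, and exclusion criterion 9 removes those who "did not follow the doctor's advice, were unable to judge the curative effect or were unable to evaluate the curative effect due to incomplete data". No completion rate is documented, however.
- **That Welch's test would settle the cycle-period analysis.** It corrects the standard error and not selective loss, as step 3 shows. If the more variable group is also strongly skewed (log-normal, log-SD 0.7), it is no better than Student's t at equal n (5.5% to 6.1% v 5.5% to 6.2%).

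**Conclusion.** The point holds in conditional form, as a low-cost improvement.

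For the hormones, the single rule in Section D probably gives up between 3 and 20 percentage points of power (77% down to 60%, against 80%). This rests on log-normal values with log-SD 0.4 to 1.0, a proportional effect, 110 per group, and comparison of levels, since Section D does not say whether levels or changes are tested. These are secondary outcomes.

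For cycle period, error above 5% needs three things together: a wider spread in one group, fewer analysed women in that same group, and a comparison involving group 1. The excess is then about 1 point at 99 v 110 and 4 points at 77 v 110, under the assumed SDs of 15 and 5 days.

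The change is still worth making, because Welch's test costs essentially nothing when groups are balanced. Fixing the scale and the test in advance also removes a choice that could otherwise be made after seeing the data.

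**What to change.** In Section D:
- Analyse FSH, LH, E2 and AMH on the natural-log scale. Report geometric mean ratios between groups with 95% CIs, and describe each group by median and quartiles. State the rule for values below the assay limit, because the documents give no limit.
- For two-group comparisons of untransformed quantities, replace Student's t with Welch's test.
- Do not present Welch's test as the remedy for cycles that are missing because they are long. How a woman without a completed cycle enters the analysis has to be settled separately.

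The cost is a few sentences of wording, with no new data and no extra participants. The one downside is that hormone effects read as ratios and not as differences in concentration. A rank test would recover most of the lost power, but it does not give an estimate of effect as direct as the geometric mean ratio.

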## **C. TECHNICAL ROUTE**

### **Screening Period (Day -30~0)**

- a) The researcher explained the research situation and informed the subjects, and the subjects signed the informed consent;
- b) Evaluate whether subjects can enter the study according to the inclusion and exclusion criteria;
- c) Collect basic information, medical history (including menstrual history, pregnancy and birth history) and demographic data, conduct routine physical examination (heart rate, blood pressure, height, weight); and irregular menstrual symptoms and scoring
- d) On the 2nd to 3rd day of the menstrual cycle (basic day), draw venous blood to check FSH, LH, E2, prolactin (PRL), testosterone (T), and AMH;
- e) Liver and kidney function;
- f) Pelvic ultrasound: on the 1st to 3rd day after menstruation is clean, after disinfection of the vulva, transvaginal ultrasound is performed to count bilateral ovarian AFC, breast ultrasound;
- g) The investigator and the subject agree on the time of the next follow-up visit.

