**Follow-up 3 (the third month after taking the medicine, equivalent to the end of the third month)**

- a) Ask and record adverse events that have occurred since enrollment;
- b) perform routine physical examinations (heart rate, blood pressure, weight);
- c) Ask the patient about the current menstruation and irregular menstruation symptoms, (or pregnancy), perform symptom scores, and evaluate the effectiveness of the drug;
- d) FSH, LH, E2, PRL, T, AMH (blood draw on day 2-3 of menstruation);
- e) Liver and kidney function;
- f) Pelvic ultrasound (bilateral ovarian AFC) examination, breast ultrasound;
- g) Subject returns untaken medication and checks (including used medication packaging) and filled diary card.

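### FSH, LH, E2, AMH and AFC are measured at screening and at month 3, but groups are compared only with unadjusted tests; ANCOVA that keeps women without a screening value would usually be more precise

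*Combined protocol and SAP*

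**What the plan says.** Section D (Statistics Analysis) gives one sentence on testing: "Statistical significance was assessed using unpaired Student's t-test or chi-square test". It names no covariate, no regression model and no rule for missing values.

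Section B lists the secondary outcomes. Hormones are given as "Sex hormone levels: mainly FSH, LH, E2 and AMH", and AFC as "Changes in AFC in pelvic ultrasonography". On the natural reading, hormones are compared on the month-3 value and AFC on the difference from screening.

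Section C schedules both measurements twice.

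- **Screening Period, items d and f:** "On the 2nd to 3rd day of the menstrual cycle (basic day), draw venous blood to check FSH, LH, E2", with AMH in the same draw; and, shortly after a menses ends, "transvaginal ultrasound is performed to count bilateral ovarian AFC".
- **Follow-up 3, items d and f:** "FSH, LH, E2, PRL, T, AMH (blood draw on day 2-3 of menstruation"; and "Pelvic ultrasound (bilateral ovarian AFC) examination", for which no cycle timing is given.

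The screening window is 30 days. Inclusion criterion 2 in Section B admits "Patients with oligomenorrhea or oligomenorrhea or menopause within three months", so some eligible women may have no menses in that window on which to time the screening measurements.

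**The concern.** A screening value that predicts the month-3 value explains part of the variation between women. A t-test on month-3 values ignores it. A t-test on change uses it, but fixes its coefficient at 1 whether or not the data support that. ANCOVA estimates the coefficient. What is at stake is the width of the confidence intervals for five secondary outcomes, from data the trial already plans to collect.

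Two features of this trial complicate a routine recommendation. First, if some women have no screening value, ANCOVA that drops them can be less precise than the planned test. Second, the month-3 hormone draw depends on a menses, which the treatments are intended to influence. That raises a question of bias that adjustment for the screening value does not settle.

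**Working it through.** **Inputs.** From the documents: 330 women, three randomised groups, significance level 0.05. Assumed, because the documents are silent: equal allocation (330/3 = 110 per group), two-sided tests, correlation r between screening and month-3 values of 0.3 to 0.7, ratio k of the screening SD to the month-3 SD, and fraction m of women without a screening value. The plan has no figure to reproduce, since 330 is stated without an effect size, SD, power or dropout rate. The 80% power used below is a reference point only.

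**1. ANCOVA against a t-test on month-3 values, complete data.** The variance ratio is 1 − r². With 110 per group, a difference of 0.379 SD gives the t-test 80% power.

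| r | 1 − r² | Power at 0.379 SD | Equivalent n per group, 110/(1 − r²) |
|---|---|---|---|
| 0.3 | 0.91 | 84% | 121 |
| 0.5 | 0.75 | 90% | 147 |
| 0.7 | 0.51 | 98% | 216 |

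**2. ANCOVA against a t-test on change, complete data.** The variance ratio is (1 − r²)/(1 + k² − 2rk).

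| k | r = 0.3 | r = 0.5 | r = 0.7 |
|---|---|---|---|
| 0.8 | 0.78 | 0.89 | 0.98 |
| 1 | 0.65 | 0.75 | 0.85 |
| 1.25 | 0.50 | 0.57 | 0.63 |

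Example, k = 0.8 and r = 0.5: 0.75/(1 + 0.64 − 0.80) = 0.75/0.84 = 0.89. When k = r the denominator is 1 − r², so the ratio is 1.00 and there is no gain. The simpler expression (1 + r)/2 holds only when k = 1.

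**3. Some screening values missing.** Relative to a month-3 t-test on all women, complete-case ANCOVA has variance (1 − r²)/(1 − m). ANCOVA with a single fill-in value and a missing indicator has 1 − (1 − m)r². At m = 0.2:

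| r | Complete case | Power | Missing indicator | Power |
|---|---|---|---|---|
| 0.3 | 0.91/0.8 = 1.14 | 75% | 1 − 0.8 × 0.09 = 0.93 | 83% |
| 0.5 | 0.75/0.8 = 0.94 | 83% | 1 − 0.8 × 0.25 = 0.80 | 88% |
| 0.7 | 0.51/0.8 = 0.64 | 94% | 1 − 0.8 × 0.49 = 0.61 | 95% |

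The complete-case method loses to the planned t-test once m exceeds r², that is 9%, 25% and 49% at the three correlations. Simulation at m = 0.2 (20,000 trials per r) gave rejection rates of 0.046 to 0.053 under no effect for all methods. A separate simulation at m = 0.3 and r = 0.5 gave ratios of 0.85 with these women kept and 1.10 with them dropped (formulas: 0.83 and 1.07).

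For AFC, a change score also drops women without a screening value. At m = 0.2 and k = 1 its variance is 2(1 − r)/(1 − m) = 1.75, 1.25 and 0.75 on the same scale. The missing-indicator analysis therefore stands at 0.93/1.75 = 0.53, 0.80/1.25 = 0.64 and 0.61/0.75 = 0.81 of it.

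Randomisation follows screening, so whether a screening value is missing cannot depend on the assigned group. That is what makes the indicator safe here.

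**4. Selection at month 3.** A hormone value at Follow-up 3 requires a menses. For illustration, assume no hormone effect, 110 per group, a month-3 menses in 90% of one group and 70% of the other, and a correlation of 0.3 to 0.5 between the hormone and the propensity to menstruate. Across two simulations of this scenario, the month-3 t-test rejected in 9% to 19% of trials and ANCOVA in 7% to 17%, against a nominal 5%. These rates are assumptions, not estimates for this trial.

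**The case against.** The strongest reply is that unadjusted comparisons of secondary outcomes are valid under randomisation, that the same remark could be made of almost any trial with a baseline measurement, and that nothing in the documents places this trial anywhere between a halving of the variance and no gain. All of that stands. It limits the point to an inexpensive improvement of unknown size.

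The missing-screening scenario may also be overstated. Enrolment refers back to the screening results, so women without them might not be enrolled. Women with no menses at screening may also be those with none at month 3, and so be absent from the hormone comparison anyway. The more they overlap, the less the complete-case and missing-indicator analyses differ. This is fair, but keeping these women costs little and protects against the case where it matters.

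A reader might infer that only precision is at issue and that ANCOVA gives a sound hormone comparison. The documents do not support this: the month-3 draw is tied to menses, and that selection comes after randomisation.

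A reader might also go on to a log scale for hormones. No figure in the documents bears on skewness, and the scale changes what is estimated, so it is not part of this point.

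Finally, a reader might infer from the monthly amenorrhoea rates listed in the primary outcome that any one significant month would count as success. Section D sets no such rule. Which month or combination is tested is a separate question of primary-endpoint definition.

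**Conclusion.** The point holds as a recommendation about precision on five secondary outcomes. The planned tests are not wrong for being unadjusted. With complete data and 110 women per group (assumed), ANCOVA has 0.91, 0.75 and 0.51 of the variance of a month-3 t-test at r = 0.3, 0.5 and 0.7. Against a change-score t-test, the combinations of r and k tabulated give 0.50 to 0.98, and there is no gain when k = r. If women without a screening value are kept, ANCOVA is in large samples at least as precise as the month-3 t-test for any r; if they are dropped, it may not be. The actual gain cannot be determined from the documents.

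For the four hormones the gain carries a limit: women with a month-3 value are a subset selected after randomisation, and neither analysis removes the bias that may follow. The Follow-up 3 entry does not tie AFC to a menses, so this limit is not evident there.

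**What to change.** In Section D, before outcome data are seen, replace the t-test for FSH, LH, E2, AMH and AFC with wording to this effect:

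> The month-3 value of each outcome is analysed by ANCOVA on treatment group (three levels) and the screening value. A woman with no screening value is retained: the value is set to the mean over all groups combined, and an indicator of missingness is added to the model. Adjusted pairwise differences between groups are reported with 95% confidence intervals.

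Add that the number of women with a month-3 value is reported by group for each outcome. State as a limitation that month-3 hormone values exist only for women who menstruated, so those comparisons may be biased by selection after randomisation.

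The cost is a few sentences in the plan and slightly more analysis work, with no added visits, assays or participants. The change does not recover missing month-3 values. The definition of the monthly amenorrhoea test should be settled separately, with the primary endpoint.

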### **Enrollment (Day 1)**

- a) Re-evaluate whether the subjects can enter the study according to the test and examination results during the screening period, referring to the inclusion and exclusion criteria;
- b) Subjects were enrolled and received medicines according to the random number table;

c) The investigator and the subject agree on the time of the next follow-up visit.

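### The primary menstrual components are compared only by unadjusted tests; these are valid, but pre-specified adjustment for the symptom score, age and menstrual history already taken at screening could add precision at little cost.

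*Combined protocol and SAP*

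**What the plan says.** Section D gives the method in one sentence: "Statistical significance was assessed using unpaired Student's t-test or chi-square test". The threshold follows: "Probability values of less than 0.05 were considered significant". No section mentions a covariate, a regression model, analysis of covariance or a stratified test.

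The primary outcome in Section B has several parts: "Menstrual improvement in women including cycle period, menstrual volume, number of days with bleeding or spotting, monthly rates of amenorrhea". Some are quantitative and one is a monthly rate. Section B does not say whether improvement means an end value, a change or a response.

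Item c of the Screening Period (Section C) collects demographic data, medical history that includes menstrual history, and the following: "conduct routine physical examination (heart rate, blood pressure, height, weight); and irregular menstrual symptoms and scoring". None of this requires the woman to be bleeding at the time, unlike the cycle-timed hormone samples and follicle count in items d and f. The symptom score is repeated at all three follow-ups.

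On allocation, Section B says "The participants were divided randomly into 3 groups" and the Enrollment section says "Subjects were enrolled and received medicines according to the random number table". Neither states a ratio, strata or blocks.

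**The concern.** Information that plausibly predicts the outcome is collected on every woman and then left out of the comparison. An unadjusted test keeps the variation that such covariates explain in its error term. It also leaves any chance difference between arms on those covariates in the estimate. No stated design feature balances severity or age across the three arms, so the analysis is the only place where the plan could deal with it.

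At stake are some power and the credibility of any adjusted result reported later. If no covariates are named in advance, an adjusted analysis added after the data are seen can be read as selected. The trial size ("330 women with menstrual disorders were observed in a prospective multi-center randomized controlled clinical trial") comes with no effect size, variability or power, so there is no documented margin against which a loss of precision could be called unimportant.

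**Working it through.** **Inputs.** From the documents: 330 women, three groups, significance threshold 0.05, unadjusted tests. Assumed because the documents are silent: equal allocation, so 330/3 = 110 per arm; two-sided testing; 80% power as a reference; no dropout; R-squared (the share of outcome variance that the covariates explain) from 0.01 to 0.3. The plan states no power or detectable difference, so there is no figure of its own to reproduce.

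**Step 1: unadjusted reference, pairwise comparison.** In units of the outcome SD, the standard error is sqrt(2/110) = 0.135. The detectable difference is (1.960 + 0.842) x 0.135 = 0.378 SD.

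**Step 2: effect of adjustment on a quantitative component.** The standard error is multiplied by sqrt(1 - R²). The equivalent gain in women is 1/(1 - R²) - 1. Power at 0.378 SD is approximately Phi(2.802/sqrt(1 - R²) - 1.960).

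| R² | SE multiplier | SE reduction | Equivalent extra women | Detectable difference (SD) | Power at 0.378 SD |
|---|---|---|---|---|---|
| 0 | 1.000 | 0% | 0% | 0.378 | 80.0% |
| 0.01 | 0.995 | 0.5% | 1% | 0.376 | 80.4% |
| 0.04 | 0.980 | 2% | 4% | 0.370 | 81.6% |
| 0.1 | 0.949 | 5% | 11% | 0.358 | 84.0% |
| 0.2 | 0.894 | 11% | 25% | 0.338 | 87.9% |
| 0.3 | 0.837 | 16% | 43% | 0.316 | 91.8% |

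**Step 3: simulation check** (3,000 trials per setting, three covariates, 110 per arm). At R² 0.25, power was 80.6% unadjusted and 90.0% adjusted. With covariates that predict nothing it was 78.5% and 78.3%, so useless covariates cost almost nothing. With no treatment effect, over R² from 0 to 0.49, rejection rates were 4.5% to 6.2% for the t-test and 4.9% to 6.1% for the adjusted model. Neither approach is systematically off 5%.

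**Step 4: chance imbalance.** The probability that one given covariate differs by at least 0.2 SD between two arms is 2 x (1 - Phi(0.2/0.135)) = 2 x (1 - Phi(1.483)) = 13.8%; for 0.3 SD it is 2.6%. An imbalance of 0.2 SD moves the unadjusted estimate by 0.2 x sqrt(R²), with R² now for that one covariate: 0.04 SD at R² 0.04, 0.06 SD at 0.1 and 0.11 SD at 0.3, against a standard error of 0.135 SD. Given such an imbalance, the conditional type I error of the unadjusted test is 6.2% at a covariate-outcome correlation of 0.3 and 8.1% at 0.5. Given 0.3 SD, it is 9.1% and 16.4%.

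**Step 5: amenorrhea.** The multiplier sqrt(1 - R²) does not apply to a logistic model. A separate simulation (1,000 trials per setting, one covariate, treatment effects set so that chi-square power was near 80%) gave 81.0%, 86.2% and 89.2% adjusted against 79.2%, 79.5% and 79.8% for chi-square, at covariate log-odds of 0.5, 1.0 and 1.5 per SD. These settings are illustrative and do not come from the documents.

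**The case against.** The strongest reply is that this is a choice about efficiency and not an error. Randomisation makes the unadjusted comparison valid, and ordinary chance imbalance is already reflected in its standard error. That stands. A reader might infer from the 13.8% figure that the planned tests are biased or exceed their nominal error rate. They do not: the conditional error rates in Step 4 apply only to trials in which the imbalance occurred, and the typical shift is below one standard error.

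A second reply is that nothing in the documents shows that these covariates predict anything. That also stands. Age is confined by eligibility to 25 to 40, and body mass index (derivable from height and weight, though not named) may be only weakly related to menstrual outcomes. If together they explain 1% to 4% of the variance, the gain is 0.4 to 1.6 points of power. The screening symptom score and the menstrual history are the likelier sources of benefit, which is why the fix rests on them. The text gives neither the score's items nor its range. If it contains cycle or volume items, it partly duplicates the menstrual-history value, which is harmless in the model.

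A third reply is that the model cannot be written until improvement is defined and a rule exists for women with no bleed, who have no obvious cycle or volume value. That is true, but the t-test needs the same decisions. Once a component's own baseline value is in the linear model, the treatment estimate is the same whether the outcome is coded as end value or change.

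**Conclusion.** The concern holds as an improvement worth making, not as a flaw that invalidates the analysis. Section D names only unadjusted tests, screening supplies usable baseline data, and no stratification is stated.

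The size is uncertain. Under equal allocation, the standard error of a quantitative component falls by about 0.5% to 2% at R-squared 0.01 to 0.04, and by 5%, 11% or 16% at 0.1, 0.2 or 0.3. No gain for amenorrhea can be read from those figures. It is tempting to say flatly that precision is being lost; the documents support only that it may be, because they give no R-squared and the true value could be near zero. The case for acting is that the possible gain is useful, the cost is small, and naming covariates in advance removes any question of later selection.

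**What to change.** Before any outcome data are seen, amend Section D as follows.

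- **Quantitative primary components:** the main analysis of each is a linear model on treatment group (three levels), screening symptom score and age. Add the screening menstrual-history value of that component where it is recorded.
- **Amenorrhea:** a logistic model with the same covariates at one named month, or a repeated-measures version over the three months. The text must say which, because the outcome is a monthly rate. Show the crude proportions beside the adjusted odds ratio, since the two describe different quantities.
- **Body mass index:** optional.
- **Supporting analyses:** keep the t-test and chi-square results.
- **Missing covariates:** state in advance how missing screening values are handled, so that women are not dropped from the main analysis.

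The cost is a few more lines of plan and a little more analysis work. No new visits, measurements or participants are needed. The month used for amenorrhea and the definition of improvement must be settled first, as they must for any analysis of these outcomes.
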